4.4.2. Adverse Events

All AEs will be coded using the MedDRA coding system version 19.0 and displayed in tables and data listings using system organ class (SOC) and preferred term (PT) based on Safety Population.

Analyses of AEs will be performed for those events that are considered treatment-emergent, where treatment-emergent is defined per protocol as any AE with onset after the first administration of tagraxofusp through 30 days after the last dose of tagraxofusp, or any event that was present at baseline but worsened in intensity or was subsequently considered drug-related by the Investigator through 30 days after the last dose of tagraxofusp.

Tabulations of the number and percentage of patients with any treatment-emergent AE (TEAE), common AEs (defined as occurring in $\geq 10\%$ of the study sample [overall for summaries by dose, within each disease for summaries by disease]), with any TEAE assessed by the Investigator as related to treatment, with any TEAE with severity \geq Common Terminology Criteria for Adverse Events (CTCAE) Grade 3, with any serious adverse event (SAE), with any AE leading to discontinuation of study treatment, with any AE to dose reduction, with any AE leading to dose interruption, with any AE leading to death, with any AE leading to death within 30 days, and with any AE leading to death within 60 days will be summarized as described in [Section 3.5](#). An overall summary of the incidence of TEAEs will also be provided.

In these tabulations, each patient will contribute only once (ie, the most related occurrence or the most intense occurrence) to each of the incidence rates in the descriptive analysis, regardless of the number of episodes. Treatment-emergent AEs (TEAEs) are summarized by patient incidence rates; therefore, in such tabulations, a patient contributes only once to the count for a given SOC or PT. For tabulations that include classification by relationship to study treatment, AEs with missing relationship will be considered related to study drug.

By-patient tabulations will also be presented for patients who died, SAEs, AEs leading to study drug discontinuation, AEs with CTCAE Grade 3, and AEs with CTCAE Grade 4.

Analysis of AEs over time will be conducted by presentation of TEAE incidence by cycle. For this analysis, incidence per cycle will be based on the onset of a particular PT event within the cycle, where onset is indicated by first or repeat occurrence or increase in severity of the event within that cycle. This analysis will be conducted by maximum CTCAE Grade for each PT. AEs over time will also be presented by cycle for the incidence of TEAE leading to treatment discontinuation, dose reduction, and dose interruption by SOC and PT.

AEs of special interest (AESIs) will be determined using MedDRA version 19.0 standardized medical queries (SMQs), high-level terms, or PTs, as follows:

- Possible hypersensitivity events, based on the SMQ Hypersensitivity (broad search).
- Vascular capillary leak syndrome (CLS), in addition to PTs of hypoalbuminaemia, blood albumin decreased, and proteinuria.
- Visual acuity, based on the MedDRA PTs related to vision changes.
- Post-transplantation veno-occlusive disease, based on the MedDRA PTs pulmonary veno-occlusive disease and veno-occlusive liver disease.
- Possible drug-induced liver injury events, based on the SMQ drug-related hepatic disorders – comprehensive search (broad search).

Summary tables of AESIs will report AESI by PT, causality, severity grade, seriousness, and whether AESI led to discontinuation of study treatment. AESIs will also be included in data listings.

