- 7 Morphology and WBC differential /blast count on aspirate. In general, bone marrow aspirates and biopsies will be performed at the end of C1 and C4 and then every 12 weeks (± 7 days) thereafter. Bone marrow evaluation should also be performed at End of Treatment; if a bone marrow evaluation was performed within 4 weeks prior to the end of treatment, a repeat evaluation does not need to be performed at this time, unless clinically indicated.
- 8 Bone marrow aspirate and imaging studies are to be repeated at the end of C1 and C4 and then every 12 weeks (± 7 days) thereafter.
- 9 Imaging studies will be performed at the end of C1 and C4 and then every 12 weeks (± 7 days) until there is evidence of relapsed or progressive disease. Abdominal scan is required; evaluation of chest/pelvis may be obtained at the Investigator's discretion. Scan must include measurement of spleen and liver volume. Imaging studies should also be performed at End of Treatment; if imaging was performed within 4 weeks prior to the end of treatment, a repeat evaluation does not need to be performed at this time, unless clinically indicated. Whenever clinically feasible, it is strongly requested that the same imaging modality (MRI or CT) at both baseline and subsequent timepoints be utilized for any given patient throughout their evaluation on-study.
- 10 Peripheral blood (serum) samples (10 mL) will be collected for the detection of tagraxofusp reactive antibodies at the completion of every cycle and at specified points thereafter.
- 11 Patients will be followed for survival approximately every 90 days, until assessment of the primary objective for the study is complete for all treated patients; please consult the appropriate protocol section for description of situations in which survival and other data may be collected following study completion. Patients who undergo SCT will be followed for the occurrence of veno-occlusive disease as part of long-term follow-up. A blood sample for immunogenicity studies will be collected at least 16 weeks to up to 20 weeks after the last tagraxofusp dose.
- 12 Premedications administered 60 minutes (± 15 minutes) before tagraxofusp treatment: Diphenhydramine 50 mg IV (or an equivalent dose of another H1-histamine antagonist); acetaminophen 650 mg orally (or equivalent dose of paracetamol); methylprednisolone 50 mg IV (or an equivalent dose of another corticosteroid); famotidine 20 mg IV (or an equivalent doses of another H2-histamine antagonist).

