13.1.1 Adverse Event (AE)

An AE is any untoward medical occurrence in a study patient who is administered a medicinal product (drug or biologic); the event may or may not have a causal relationship with the medicinal product. Examples of AEs include, but are not limited to the following:

- Clinically significant symptoms and signs including:
 - Worsening of signs and symptoms of the disease under study; disease progression without worsening of signs and symptoms as assessed by bone marrow aspiration or other methods should not be reported as AEs.
 - Signs and symptoms resulting from drug overdose, abuse, misuse, withdrawal, sensitivity, dependency, interaction, or toxicity.
 - All possibly related and unrelated illnesses, including the worsening of a preexisting illness.
 - Injury or accidents. Note that if a medical condition is known to have caused the injury or accident (hip fracture from a fall secondary to dizziness), the medical condition (dizziness) and the outcome of the accident (hip fracture from a fall) should be reported as 2 separate AEs.
- Abnormalities in physiological testing or physical examination findings that require clinical intervention or further investigation (beyond ordering a repeat confirmatory test).
- Laboratory abnormalities that meet any of the following (Note: merely repeating abnormal test, in the absence of any of the below conditions, does not constitute an AE. Any abnormal test result that is determined to be an error does not require reporting as an AE):
 - Test result that is associated with accompanying symptoms
 - Test result that requires additional diagnostic testing or medical/surgical intervention
 - Test result that leads to significant additional concomitant drug treatment or other therapy
 - Test result that is considered to be an AE by the Investigator or Sponsor

Note that veno-occlusive disease occurring post-SCT and any changes in visual acuity and/or color vision will be followed as AEs of special interest.

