13.5 Documentation and Reporting of Adverse Events by Investigator

The Investigator is to report all directly observed AEs and AEs spontaneously reported by the patient using concise medical terminology. In addition, each patient will be questioned about AEs at each clinic visit following initiation of treatment. The question asked will be "Since your last clinic visit have you had any health problems?" or a similar question to assess health status.

The AE reporting period for this study begins after provision of written informed consent and ends 30 days after the last tagraxofusp infusion. All AEs are to be reported on the AE eCRFs.

All AEs that occur in study patients during the AE reporting period must be reported to the Sponsor, whether or not the event is considered study drug-related. In addition, any untoward

event that occurs beyond the AE reporting period that the Investigator assesses as related to the investigational product should also be reported as an AE.

Each AE is to be classified by the Investigator as serious or non-serious. This classification of the gravity of the event determines the reporting procedures to be followed. If a SAE occurs, reporting will follow local and international regulations, as appropriate.

For any event that meets one of the SAE criteria, the Investigator must notify the Safety Contact **within 24 hours** of the knowledge of the occurrence. To report the SAE, complete the SAE form and email to the Safety Contact (email address listed below) within 24 hours of awareness.

Safety Contact Information: E-mail: [REDACTED]

Each SAE should be followed until resolution, or until such time as the Investigator determines its cause or determines that, it has become stable.

Within 24 hours of receipt of follow-up information, the Investigator must update the SAE form and submit any supporting documentation (e.g., patient discharge summary or autopsy reports) to the Safety Contact via e-mail. All SAEs are also to be recorded in the eCRF.

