14.4 Analyses of Safety Data

Safety assessments include DLTs, AEs, SAEs, physical examinations, vital sign measurements, ECGs, clinical laboratory evaluations, and reasons for treatment discontinuation due to toxicity.

Treatment-emergent AEs through 30 days after the last tagraxofusp infusion will be summarized by Medical Dictionary for Regulatory Activities (MedDRA™) Version 13.1 (or higher) System Organ Class and preferred term. The incidences and percentages of patients experiencing each AE preferred term will be summarized with descriptive statistics. AEs will also be summarized by NCI CTCAE, Version 4.03 (or higher), grade and by causality (relationship to study drug). DLTs, Grade 3-4 AEs, SAEs, and AEs resulting in dose modification or treatment discontinuation will also be summarized by preferred term.

Laboratory results will be classified according to NCI CTCAE, Version 4.03. Laboratory results not corresponding to an NCI CTCAE term will not be graded. Incidences of laboratory abnormalities will be summarized with descriptive statistics.

Vital signs, physical examination results, and ECGs will be summarized with descriptive statistics.

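### SAP 4.4.2 closes adverse event analyses 30 days after the last dose and makes no exception for post-transplant veno-occlusive disease, which the protocol follows for longer

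*SAP*

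**What the plan says.** **Analysis window.** SAP 4.4.2 states that "Analyses of AEs will be performed for those events that are considered treatment-emergent". It defines these as "any AE with onset after the first administration of tagraxofusp through 30 days after the last dose of tagraxofusp", plus events present at baseline that worsen or are later judged drug-related, again only through day 30. Protocol 14.4 uses the same limit: "Treatment-emergent AEs through 30 days after the last tagraxofusp infusion will be summarized by" MedDRA class and term.

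**VOD as an AESI.** The list in SAP 4.4.2 includes "Post-transplantation veno-occlusive disease, based on the MedDRA PTs pulmonary veno-occlusive disease and veno-occlusive liver disease". No separate time window is given. AESI summary tables are planned by preferred term, causality, grade, seriousness and discontinuation, and AESIs also go into data listings. SAP 4.4 bases safety analyses on the Safety Population, meaning everyone who received at least one dose.

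**Collection.** Protocol 13.1.1: "Note that veno-occlusive disease occurring post-SCT and any changes in visual acuity and/or color vision will be followed as AEs of special interest". Protocol Table 3 (footnote 12) and Table 5 (footnote 11), both copied into the SAP flow charts: "Patients who undergo SCT will be followed for the occurrence of veno-occlusive disease as part of long-term follow-up". The same footnotes set the rhythm of that follow-up: "Patients will be followed for survival approximately every 90 days".

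**Reporting period.** Protocol 13.5 says that the adverse event reporting period "ends 30 days after the last tagraxofusp infusion". Section 13 and 13.5 add that later events are reported if the investigator judges them related.

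**The concern.** This AESI is defined by a procedure that normally comes after tagraxofusp has stopped; SAP 4.1 counts transplants since discontinuation. The protocol therefore looks for VOD in long-term follow-up, while the SAP stops counting at day 30 after the last dose. The SAP does not say how a VOD found later is to be summarized.

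The contrast with efficacy is awkward. SAP 4.3.2 and 4.3.3 carry duration of response and progression-free survival through transplant, and SAP 1.2.5.1 uses bridge to transplant to support the primary endpoint. Follow-up after transplant thus counts towards benefit, while the one AESI tied to transplant is cut off.

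Characterizing the safety profile is the first-listed Stage 3A objective. A zero in the planned table would not tell the reader whether transplanted patients were followed and had no VOD, or whether events fell outside the window.

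**Working it through.** **1. Follow the rule as written.** Take a VOD with onset on day 45 after the last dose.
- Judged related: reportable under Protocol 13 and 13.5, but not treatment-emergent under SAP 4.4.2, so absent from the AESI tables.
- Judged unrelated: outside the general reporting period of Protocol 13, 13.2 and 13.5, yet within the VOD follow-up of Tables 3 and 5. These passages need reconciling. The event is absent from the AESI tables here too.

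This step needs no assumption about timing.

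**2. Condition for being counted.** Let L be days from last dose to transplant and V be days from transplant to VOD onset. A post-treatment VOD is counted only if L + V ≤ 30. For V = 14 the transplant must come by day 16 (30 − 14); for V = 21, by day 9 (30 − 21). If L exceeds 30, nothing is counted.

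**3. Share counted.** The documents give neither L nor V, so there is no figure of the plan's own to reproduce. Both are assumed here: lognormal, log-SD 0.5, 400,000 draws per cell.

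| Assumed median L | V median 7 d | V median 14 d | V median 21 d |
|---|---|---|---|
| 7 d | 97% | 79% | 53% |
| 14 d | 79% | 51% | 28% |
| 28 d | 32% | 15% | 7% |
| 42 d | 11% | 4% | 2% |
| 60 d | 3% | 1% | 0.3% |

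Uniform distributions, again assumed, can be checked by hand with V on 7–21 days:
- L on 14–60 days: favourable area 9 × 9 / 2 = 40.5; total area 46 × 14 = 644; 40.5/644 = 6.3%.
- L on 7–30 days: favourable area 2 × 14 + 14 × 14 / 2 = 126; total area 23 × 14 = 322; 126/322 = 39%.

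The result depends almost entirely on the assumed timing.

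**4. Number at risk.** The only post-treatment transplant count in the documents is 1 patient, reported among the 4 marrow complete responders in 36 CMML patients (Protocol 1 and 14.2.1). It is therefore a minimum. 1/36 = 2.8%, exact 95% interval 0.07% to 14.5%.

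**5. Denominator.** With 1 transplanted patient in 36, one VOD would be shown as 1/36 = 2.8% on the Safety Population, against 1 of 1 among those transplanted after tagraxofusp.

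**6. Expected count with the window removed.** Expected events = N × P(transplant) × P(VOD given transplant). Take N = 40 (the planned Stage 3A size, two cohorts of about 20) and an assumed VOD risk of 5% to 20%:
- Transplant at 1/36: 40 × (1/36) × 0.05 = 0.06, up to 40 × (1/36) × 0.20 = 0.22. P(no events) is 95% to 80%.
- Transplant at 14.5%: 40 × 0.145 × 0.05 = 0.29, up to 40 × 0.145 × 0.20 = 1.16. P(no events) is 75% to 31%.

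A low count is therefore likely whichever window is used.

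**The case against.** The best defence is that the SAP is ambiguous rather than wrong. The AESI paragraph does not repeat the treatment-emergent restriction, although the paragraph before it uses that term. SAP 4.4.2 also tabulates adverse events leading to death within 60 days, without a stated reference date, so 30 days may not bound every table. This does not remove the problem. The general sentence governs adverse event analyses unless an exception is made, and none is.

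A second defence is that AESIs go into by-patient listings with no 30-day limit restated, which with so few transplants is informative. That is fair, and it answers anyone who might infer that the long-term VOD follow-up feeds no output at all. A listing still gives neither a rate nor a number at risk.

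A reader might also infer that the window closes before most VOD can occur, so that the table is near zero by construction. The documents do not support this:
- They give no transplant or VOD timing, and some assumed timings capture most events.
- The AESI is found by preferred term, so an on-treatment VOD would count. Three patients had an allogeneic transplant before the study, and the exclusion covers only the 3 months before entry.
- Few transplants would keep the count low anyway.

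Nor do the documents show that a VOD attributed to the transplant need never be reported. Protocol 13.1.1 and the Table 3 and 5 footnotes can be read as a specific rule alongside the general 30-day period.

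**Conclusion.** The gap is real, and it rests on the text alone: under SAP 4.4.2 as written, VOD with onset after day 30 is left out of the AESI summary tables, drug-related or not, although the protocol plans to look for it. The denominator also mixes in patients who were never at risk of post-transplant VOD.

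Its size cannot be stated from the documents. The share missed is total if the transplant falls more than 30 days after the last dose. Otherwise, under the assumed medians in the table, it runs from about 3% to over 99%. The number of patients concerned is probably small. This is a reporting gap in a descriptive safety summary; it touches no sample size, power or error rate. It is worth closing because the repair is cheap and a zero in the planned table would be hard to interpret.

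**What to change.** In SAP 4.4.2, add a separate summary of post-transplant VOD:
- count events from first dose through last follow-up, regardless of the treatment-emergent window and of causality;
- use patients who had a transplant after tagraxofusp as the denominator;
- show days from last dose and days from transplant for each event;
- show separately any VOD in patients whose only transplant was before the study;
- state that this table is not limited to treatment-emergent events.

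If any patients remain in follow-up, reconcile Protocol 13, 13.2 and 13.5 with the VOD follow-up in Tables 3 and 5. SAP 5 reports that Stage 3A enrolment was not continued and that analysis follows once all patients have exited, so this second step may add little. The SAP change remains useful until database lock.

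The cost is one sentence and one small table. The protocol already provides for VOD follow-up, and SAP 4.1 already counts transplants after discontinuation. The downside is that the table will include cases caused by the transplant itself and may look less favourable; showing both time intervals helps the reader judge those.

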8.2 Study Treatment Administration Schedule

Patients will receive 12 mcg/kg of tagraxofusp by IV infusion once daily for 3 consecutive days (or 3 doses over a period not to exceed 10 days if postponement is required to allow for toxicity resolution) of a cycle in the absence of PD or other withdrawal criteria.

A treatment cycle is 21 days in C1-4 and 28 days in C5 and beyond.

The total per-patient dose is calculated based on patient body weight in kg at baseline (C1D1). This dose will be recalculated if there is a 10% or greater change from baseline in body weight.

The first cycle of tagraxofusp must be administered in the inpatient setting, with hospitalization beginning the day of the first infusion of tagraxofusp (or a prior day) and ending approximately 24 hours after the last infusion of tagraxofusp. Subsequent cycles of tagraxofusp can be administered in the inpatient setting or in a suitable outpatient ambulatory care setting that is equipped for intensive monitoring of patients with hematopoietic malignancies undergoing treatment, per the Investigator's discretion, institutional guidelines, and capabilities. Patients will be monitored for at least 1 hour (or longer at the Investigator's discretion) following the administration of each infusion of tagraxofusp in Cycle 2 and beyond.

Patients with evidence of ongoing disease control during treatment (without evidence of clinically significant PD or intolerable toxicity) may receive repeated cycles of tagraxofusp even if an overall response, in the judgment of the Investigator, is not attained.

Refer to [Section 8.2.1](#) for details regarding required pre-medication, patient monitoring procedures, and dose modification procedures for the management of tagraxofusp-related toxicity.

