1.1.2. Study Design

Study STML-401-0314 was initially designed as a 2-stage, non-randomized, open-label, multicenter study of tagraxofusp in patients with subtypes of advanced, high risk MPNs. Initially in this study, patients with CMML and myelofibrosis (MF), as well as systemic

mastocytosis (SM) and advanced symptomatic chronic eosinophilic leukemia, including primary eosinophilic disorders (PED) were eligible for enrollment.

In Stage 1, which is complete at the time of this Statistical Analysis Plan (SAP), only patients with CMML and MF were enrolled. The primary objective of Stage 1 was to establish the maximum tolerated dose (MTD) or the maximum tested dose (MTeD) at which multiple dose-limiting toxicities (DLTs) were not observed. In Stage 2, further characterization of the safety and initial assessment of clinical activity at the recommended phase 2 dose (RP2D) were intended in patients with MF and CMML, with an initial planned sample size of 18 patients in each cohort, then extended to approximately 30 patients in each cohort. Enrollment in Stage 2 is closed.

In Stage 1, 9 patients (5 with CMML and 4 with MF) received tagraxofusp at doses of [REDACTED] via intravenous (IV) infusion on days 1-3 every 21 days for Cycles 1-4, every 28 days for Cycles 5-7, and every 42 days for Cycles 8 and beyond. No MTD was identified in Stage 1 and the MTeD was 12 µg/kg which was considered the RP2D. In Stage 2 of this study, patients received tagraxofusp at the RP2D, 12 µg/kg, on the same schedule as Stage 1. Stage 2 primarily included patients with CMML and MF; 1 SM patient was treated during Stage 2 at the RP2D.

Based on preliminary clinical activity observed and increasing scientific and clinical knowledge of CMML, Stage 3A was added by protocol amendment 7, dated October 21, 2019. Stage 3A enrolled 2 populations of patients with CMML-1 and CMML-2:

1. Previously untreated patients who are high risk and not expected to benefit from hypomethylating agents (HMAs) (previously untreated patients; approximately 20 patients), and
2. Patients who are primary or secondary failures to first-line therapy, including HMAs, hydroxyurea (HU), or intensive chemotherapy (first-line failure patients; approximately 20 patients).

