1.2.1.2. Stage 2 Study Design

Stage 2 was a non-randomized, open-label multicenter study stage to determine the safety and efficacy of single-agent tagraxofusp in patients with CMML and separately in patients with MF. Tagraxofusp was administered as a 15-minute IV infusion once daily on Days (D) 1 to 3 of a 21-day cycle (Cycles [C] 1 to 4); and on D1 to 3 of a 28-day cycle (C5 and beyond). The dosing period may have been extended for dose delays up to D10 of each cycle. Patients could continue to receive treatment with tagraxofusp as long as, in the opinion of the Investigator, benefit from treatment was indicated.

Beginning with Protocol Amendment 7, up to approximately 20-25 additional patients with MF were to be enrolled in Stage 2 to further elucidate the safety and efficacy profile of tagraxofusp in this patient population. Thus, across all study stages, approximately 50-55 patients with MF could be enrolled.

Note: CMML and MF patients consented and enrolled with Amendment 6 or prior, and currently on active treatment or in survival follow-up, continued to be followed according to the

schedule of events in Amendment 6. These patients were not reconsented under Amendment 7 or beyond.

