1.2.1.3. Stage 3A Study Design

Stage 3A is a 2-arm, non-randomized, open-label multicenter study stage in patients with CMML intended to identify clinically important responses that connote clinical benefit and potential endpoints, as well as gather data on CD123 expression on pDCs and monocytes in CMML.

Stage 3A includes 2 populations of patients with CMML: those with CMML-1 or CMML-2 who are refractory/resistant/intolerant to HMs, or HU, or intensive chemotherapy; and patients with treatment naïve CMML-1 or CMML-2 with molecular features associated with a poor prognosis who are not expected to benefit from HMs.

In Stage 3A patients were administered tagraxofusp at a dose of [REDACTED] as a 15-minute IV infusion once daily on D1 to 3 of a 21-day cycle (C1 to C4) and then on D1 to 3 of a 28-day cycle (C5 and beyond). The dosing period may be extended for dose delays up to D10 of each cycle.

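### The by-cycle adverse event table ignores cycle length, so an event with a constant daily rate shows a false step up at Cycle 5 among patients who start it

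*SAP*

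**What the plan says.** SAP 4.4.2 states: "Analysis of AEs over time will be conducted by presentation of TEAE incidence by cycle". The counting rule is that "incidence per cycle will be based on the onset of a particular PT event within the cycle"; a first occurrence, a repeat or a worsening all count as onset. The same layout is used for events leading to discontinuation, dose reduction and interruption. The section gives no denominator for these tables and no adjustment for days observed. The only general rule, in SAP 3.10, takes percentages from the total population. Under SAP 3.5, safety summaries are shown by dose, and by disease and stage.

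Cycle lengths are described as follows.

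- Protocol 8.2: "A treatment cycle is 21 days in C1-4 and 28 days in C5 and beyond".
- Stage 1, SAP 1.1.2: "every 21 days for Cycles 1-4, every 28 days for Cycles 5-7, and every 42 days for Cycles 8 and beyond".
- Stage 2: SAP 1.1.2 says patients were treated "on the same schedule as Stage 1", which implies 42 days from Cycle 8. SAP 1.2.1.2 instead gives a "21-day cycle (Cycles [C] 1 to 4); and on D1 to 3 of a 28-day cycle (C5 and beyond", with no 42-day interval.
- Stage 3A: SAP 1.2.1.3 and Protocol 5.1 stop at 28 days, although the overview in Protocol 1 places Stage 3A on the Stage 1 schedule.

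Three doses are planned in every cycle, whatever its length.

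**The concern.** A longer cycle gives more days in which an event can start. A percentage of patients with onset in the cycle therefore mixes risk with length of observation. For events whose onsets are spread through the cycle, the table would show a step at Cycle 5, and another at Cycle 8 where the 42-day interval applies, even if the daily risk never changed.

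This matters because the table is the SAP's stated analysis of adverse events over time, and Protocol 4.4 reports that toxicity has not been seen to accumulate. A reader checking that statement would look here. An artefact at Cycle 5 could be read as late toxicity, and a real change at the same point could not be told apart from it. In the by-dose tables, stages share the 12 µg/kg column, so a Cycle 8 cell can combine windows of 28 and 42 days.

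**Working it through.** The plan states no figure for this analysis, so there is none to reproduce. The cycle lengths (21, 28, 42 days) come from the sections cited. The event rates and dropout rates are assumptions, shown as ranges.

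**Step 1: patients who start the cycle, constant rate per day.** If p is the incidence in 21 days, incidence in a cycle of L days is 1 − (1 − p)^(L/21). For p = 10%: 1 − 0.9^(28/21) = 13.1%, and 1 − 0.9^(42/21) = 1 − 0.81 = 19.0%.

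| 21 days | 28 days | 42 days | ratio 28/21 | ratio 42/21 |
|---|---|---|---|---|
| 2% | 2.7% | 4.0% | 1.33 | 1.98 |
| 5% | 6.6% | 9.8% | 1.32 | 1.95 |
| 10% | 13.1% | 19.0% | 1.31 | 1.90 |
| 20% | 25.7% | 36.0% | 1.29 | 1.80 |
| 30% | 37.8% | 51.0% | 1.26 | 1.70 |
| 50% | 60.3% | 75.0% | 1.21 | 1.50 |

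The pattern is flat within Cycles 1-4 and within Cycles 5-7, with steps between.

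**Step 2: events tied to dosing.** If the risk belongs to the three-dose course and onset falls inside 21 days, every cycle captures the same risk and the ratio is 1.00. Capillary leak syndrome is an example: Protocol 8.2.3.1 places it 3 to 8 days after treatment starts.

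**Step 3: total-population denominator.** With dropout q per cycle, the percentage in cycle c is (1 − q)^(c−1) times the step 1 value. For p = 10%, with 42 days at Cycle 8:

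| q | C1 | C4 | C5 | C8 |
|---|---|---|---|---|
| 5% | 10.0 | 8.6 | 10.7 | 13.3 |
| 10% | 10.0 | 7.3 | 8.6 | 9.1 |
| 20% | 10.0 | 5.1 | 5.4 | 4.0 |
| 30% | 10.0 | 3.4 | 3.1 | 1.6 |

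The rise from Cycle 1 is cancelled once fewer than 10/13.1 = 76% of patients start Cycle 5, or 10/19.0 = 53% start Cycle 8. The local step from Cycle 4 to Cycle 5 survives at 5% to 20% dropout and is gone at 30%.

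**Step 4: final cycle.** Treatment-emergent events run to 30 days after the last dose, about Day 33 of a patient's last cycle if dosing is on Days 1-3. Incidence becomes (1 − q) × f(L) + q × f(33), where f is the step 1 formula. For p = 10% and q = 10% to 30%, the 28/21 ratio falls from 1.31 to 13.3/10.5 = 1.27 and then 13.8/11.6 = 1.19. The 42/21 ratio falls from 1.90 to 1.77 and then 1.54. The effect shrinks but remains.

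**Step 5: person-time.** For p = 10%, −ln(0.9)/21 = 0.502 events per 100 patient-days. The rate is the same at 28 and 42 days, so a constant-rate event is flat.

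**The case against.** The strongest defence is that a cycle is a natural unit for this drug. Every cycle carries the same three planned doses, and much of the expected toxicity follows dosing closely. For such events, incidence per cycle is incidence per course and needs no correction. That stands. A reader might infer that any event with a constant rate will appear to rise with time on drug. The documents do not support this: it holds only for a rate constant per day, and they establish such a rate for no named event.

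Second, the denominator is unstated. If SAP 3.10 governs, dropout can flatten or reverse the trend, so a rise is not guaranteed. This also stands, but it is a second distortion acting against the first, not a correction. Settling the denominator alone as patients who start the cycle would expose the length effect in full.

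Third, a near-doubling has narrow support. The 42-day interval is undisputed only in Stage 1, with 9 patients, and only for those who reach Cycle 8. Stage 1 has its own column in the tables by disease and stage.

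Fourth, start delays under Protocol Table 1 can follow any cycle, including 21-day ones, so they blur the contrast and do not by themselves create a trend.

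Finally, the table is descriptive and no stated decision rests on it. SAP 5 records that Stage 3A enrolment was not continued and Stage 3B will not start. The SAP also has laboratory change over time and separate summaries of capillary leak onset and recurrence. It would go too far to call this table the plan's main test of cumulative toxicity.

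**Conclusion.** The point holds in limited form. Among patients who start the cycle, the planned table inflates incidence at Cycle 5 by about 1.21 to 1.33 fold for events with a constant daily rate and 21-day incidence between 2% and 50%. The final-cycle window reduces this somewhat. A 1.5 to 1.98 fold rise over Cycles 1-4 applies only where cycles last 42 days. Events tied to the dosing course with onset inside 21 days are not affected, and a total-population denominator with dropout can hide or reverse the step. The event and dropout rates are illustrative; the cycle lengths are the plan's own. The contradiction on the Stage 2 schedule has to be reconciled before anyone can say which Cycle 8 cells are affected. This is a cheap improvement to a descriptive table, not a flaw that invalidates the safety analysis.

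**What to change.** In SAP 4.4.2:

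- State that the denominator of each by-cycle table is the patients who start that cycle, and print that number.
- Keep the planned table, and add one of two versions beside it: onset restricted to Days 1-21 of each cycle, or events per patient-time at risk in the cycle.
- Show the added version by stage, so that different schedules are not mixed in one cell.

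Separately, reconcile SAP 1.1.2 with SAP 1.2.1.2 on the Stage 2 interval from Cycle 8, and Protocol 1 with Protocol 5.1 and 8.2 for Stage 3A.

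The cost is a little extra programming. Onsets after Day 21 are absent from the Day 1-21 version only, which for a 42-day cycle is half the window. They stay in the planned by-cycle table and the overall table. A Day 1-21 window lies within event collection even in a patient's last cycle, since collection runs 30 days past the last dose. The person-time version keeps late onsets but is a different measure from patient incidence, so it should sit beside the planned table and not replace it.
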